9	May 2019	Addition of Forts Belvoir and Myer as combined study site (FBM), recruitment from all active duty military branches affiliated with these sites, not just Army exclusive, as potential study participants. Updated power analysis.	N
10	June 2019	Moving of Focus Group activity to occur after Cohort 1 of intervention and not before program delivery per change in our Statement of Work approved by DoD. Submission of Fort Belvoir letter of support and Fort Myer Memo of Agreement.	Y, addition of Focus Group consents form (V1)

Table of Contents

1.0	Objectives	7
2.0	Background	7
3.0	Study Endpoints/Events/Outcomes.....	8
4.0	Study Intervention(s)/Interaction(s).....	8
5.0	Procedures Involved.....	9
6.0	Data Banking	21
7.0	Sharing of Results with Participants	21
8.0	Study Duration	21
9.0	Study Population	21
10.0	Vulnerable Populations	22
11.0	Number of Participants	23
13.0	Withdrawal of Participants	27
14.0	Risks to Participants.....	27
15.0	Incomplete Disclosure or Deception.....	29
16.0	Potential Benefits to Participants	29
17.0	Data Management	30
18.0	Confidentiality	31
19.0	Provisions to Monitor the Data to Ensure the Safety of Participants	34
20.0	Provisions to Protect the Privacy Interests of Participants	34
21.0	Compensation for Research-Related Injury.....	34
22.0	Consent Process	34
23.0	Setting	36
24.0	Multi-Site Research	36
25.0	Resources Available.....	37
26.0	References.....	38

PROTOCOL TITLE: SMART optimization of a parenting program for active-duty families
VERSION DATE: V10, June 2019

ABBREVIATIONS/DEFINITIONS: NA

STUDY SUMMARY

Study Title	SMART optimization of a parenting program for active-duty families
Study Design	Sequential multiple assignment randomization trial
Primary Objective	advance the “development, adaptation, efficiency or optimization, and testing of a prevention intervention by using a sequential, multiple assignment, randomized trial/SMART to test multiple components of an empirically-supported parent training prevention intervention – After Deployment Adaptive Parenting Tools (ADAPT)
Secondary Objective(s)	
Primary Study Intervention or Interaction	ADAPT, which is a Parent Management Training-Oregon (PMTO) program for military families with children ages 5-12 years old.
Study Population	Active duty families
Sample Size (number of participants)	525
Study Duration for Individual Participants	2 years

1.0 Objectives

1.1 Purpose:

The overarching goal of the "SMART Optimization of a Parenting Program for Active-Duty Families" study is to advance the “development, adaptation, efficiency or optimization, and testing of a prevention intervention by using a sequential, multiple assignment, randomized trial/SMART to test multiple components of an empirically-supported parent training prevention intervention – After Deployment Adaptive Parenting Tools (ADAPT) for active-duty families negotiating multiple deployments and high deployment OPTEMPO (an army program that provides critical responses).

2.0 Background

2.1 Significance of Research Question/Purpose:

Deployment (and particularly high deployment operational tempo/OPTEMPO) can generate family and personal stressors that disrupt supportive social relationships and functioning at home, thereby weakening the strength of our military force in the field. Stressors include separation from, and reunification with families, concerns about mobilizations and combat stressors. These stressors, in turn, are associated with reduced parenting effectiveness, marital/partner difficulties, emotion dys-regulation, and increased coercion. Coercion predicts risk for child maladjustment, as well as marital disruptions. Without effective prevention interventions, such environments may contribute to high divorce rates, child maladjustment, and reductions in service member wellbeing.

Most prevention interventions use a one-size-fits-all approach (i.e. all participants receive the same dose, format, and type of program) but this approach is often inefficient. Some families benefit from this approach but many do not. Adaptive interventions maximize efficiency, scalability, and sustainability, by providing families with a tailored dose, timing, program format, and/or sequence to improve outcomes based on their preferences and needs.

2.2 Preliminary Data:

After Deployment: Adaptive Parenting Tools (ADAPT) is a Parent Management Training-Oregon (PMTO) program for military families with children ages 5-12 years old. PMTO is a theoretically-based family of interventions with extensive research supporting efficacy and effectiveness. ADAPT was developed and tested primarily with National Guard/Reserve families. Program findings, based on 3 RCTs, indicate positive outcomes. No empirically supported parent training programs have been validated in RCTs for active duty military families with school-aged children in regular and high deployment OPTEMPO contexts.

2.3 Existing Literature:

We are proposing a Phase III Clinical trial. The SMART optimization of a parenting program for active-duty families uses an adaptive intervention strategy

to optimize an evidence-based universal prevention intervention, After Deployment Adaptive Parenting Tools/(ADAPT). SMART trials are rapidly gaining recognition within the medical and mental health fields as an innovative approach to developing adaptive treatment regimens (Almirall, Compton, Gunlicks-Stoessel, Duan & Murphy, 2012). SMARTs have been successfully implemented in diverse areas including interventions for cancer (Thall et al., 2007), autism spectrum disorders (Kasari et al., 2014), adolescent depression (Almirall et al., 2012), and alcoholism (Murphy, Lynch, Oslin, McKay, & Ten Have, 2007). SMARTs also show considerable promise in innovating intervention approaches within prevention contexts (August, Piehler, & Bloomquist, 2014).

3.0 Study Endpoints/Events/Outcomes

3.1 Primary Endpoint/Event/Outcome:

In this study, we will compress and test a variety of formats, sequences, and doses of ADAPT. We will provide two 'first line' ADAPT programs and two slightly more intensive booster ADAPT programs for families who do not 'respond' to the first line intervention. Adaptive intervention strategies involve decision rules that specify how the type or intensity of an intervention should change depending on participants' response on a predetermined indicator of initial progress within an intervention.^{56, 57, 58} Within a SMART, a measure of initial response is used following delivery of an intervention in order to evaluate each families' need for further intervention programming. In this way, programming is tailored to meet the needs of individual families by providing additional services only to those families who are likely to benefit. This measure of initial response is referred to as a primary tailoring variable. In the proposed study, the primary tailoring variable is parental locus of control, a key variable shown in our prior studies to predict change in observed parenting effectiveness, as well as change in other outcomes (PTSD symptoms, suicidality, and child adjustment).

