To address Aims 2,3,4: Among 210 SO and 315 RA families (i.e., total N=525 families) with 5-12 year-old children, we will examine effects of ADAPT modalities and sequences/timing on multiple behaviors and outcomes (i.e., (i) coercive family interactions, positive parenting, couple adjustment, and co-

parenting, (ii) parents PTSD symptoms, depression symptoms, substance use, (iii) child behavior and emotional problems, and positive adjustment, by conducting a 2-stage SMART, and (iv) document participation, satisfaction, and fidelity. To assess behaviors and outcomes, we will administer and collect a series of assessments (Table 1 appendix) at 4 timepoints.

For Aims 2, 3, and 4, we will use a 2-stage SMART design to examine the optimal sequence, dosage, and delivery formats of ADAPT for active duty military families living in a range of operational tempo contexts. We will recruit a total of 525 families living on three installations: Fort Bragg (North Carolina), Fort Campbell (Kentucky) and Forts Belvoir/Myer, with 210 families recruited from Fort Bragg and Fort Campbell and 105 from Forts Belvoir/Myer.

5.2 Study Procedures:

Subjects for this study include: (I) 525 active duty clinical trial participants recruited from 4 bases who will be randomized to first stage (brief interventions) and second stage (more intensive booster ADAPT programs for families who do not benefit from the first stage interventions); (II) Twelve current study families (N = 24) who will participate in focus groups; (III) 525 children participants between the ages of 5-12 of clinical trial participants who will be asked to participate in assessments only; (IV) Up to 1890 teachers who will be asked to complete the Behavior Assessment System for Children, Second Edition (BASC-3) each yr that the child is in the study (usually 3 grades)

Focus group Participants

We will hold two focus groups with study parents to inform program modifications. Each focus group will consist of 12 participants, one group Special Operations (SO) participants and one group Regular Army (RA) participants, both on Fort Bragg, NC.

Clinical Trial Participants

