All measures are listed in the table below and include: (1) The Parenting Locus of Control (PLOC); (2) The Family Interaction Task (FIT); (3) The Alabama Parenting Questionnaire (APQ-22); (4) Deviant Peer Association (PERS); (5) The Behavior Assessment System for Children, Third Edition (BASC-3); (6) Coping with Children's Negative Emotions (CCNES); (7) The UCLA PTSD-Reaction Index (PTSD-RI); (8) the Children's Depression Inventory (CDI); (9) Describing Friends; (10) PTSD Checklist (PCL); (9) Difficulties in Emotion Regulation Scale (DERS); (11) The Five Facet Mindfulness Questionnaire (FFMQ); (12) Receipt of Help (PSI); (13) Alcohol Use Disorders Identification Test (AUDIT); (14) Center for Epidemiologic Studies Depression Scale (CESD); (15) Deployment Risk and Resilience Inventory (DRRI); (16) Differential Ability Scales (DAS-7); (17) Moral Injury (MIES); (18) Parenting Mindfulness (IEM-P); Parenting Identity; (19) NIH Toolbox Flanker (EF – Inhibitory Control); (20) NIH Toolbox Peabody Picture Vocabulary Test; (21) Deviant Peer Association (TPRISK) Process measures include: satisfaction questionnaires, attendance, practice, online use, and coder ratings to measure fidelity.

(i) The PLOC will be used as the primary tailoring variable measure by all participants at 4 weeks following the start of the intervention (when condensed group or online programming is completed). The PLOC is a 22-item questionnaire that takes about 5 minutes. A link sent to each parent's email address will provide access to the questionnaire. The results of this questionnaire will determine responder status for each individual. If a parent scores below the cut-score

threshold on the PLOC or does not complete the PLOC, that family will be re-randomized to the second stage ADAPT interventions.

(ii) Context measures:

- (a) Demographic information such as gender, age, racial, and ethnic identity for parent and child;
- (b) employment;
- (c) income,
- (d) date/s and number of deployments for parents. Number and length of deployments will be assessed from 3 open-ended questions to obtain information about the extent of respondents' deployment history. Combat exposure will be measured using subscales from the DRRI, an ecologically valid instrument for assessing risk and resilience factors among military personnel participating in recent and current deployments.

(iii) Parenting practice measures:

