17.0 Data Management

17.1 Data Analysis Plan:

Analyses will be conducted in several steps, starting with preliminary and preparatory analyses including data reduction and evaluation of psychometric properties, followed by evaluation of missing data of criterion measures. For the primary efficacy evaluation aims of main effect components and the four adaptive intervention strategies we will employ standard normal theory Analysis of Covariance factorial and fractional factorial analyses to address study aims using pre-post assessment scores for parent and child adjustment constructs. To address the non-independence of subjects in the embedded adaptive intervention designs we will estimate Linear mixed models and weighted least squares regressions for estimation of the embedded adaptive intervention contrasts. Descriptive statistics (mean, range, SD) will be used in reporting participation, satisfaction (for fathers and mothers), and implementation fidelity (for each provider and the group of ADAPT providers).

17.2 Power Analysis:

First, we chose a power convention of .80 with a two-sided alpha level of .05 to reduce the probability of obtaining a false positive improvement or intervention effect rejecting the null when it is true (Type-I error at 5% chance). Second, we powered the study to detect small to medium effect sizes for the first and second stage randomizations. The first stage randomization is allocated with a 1:1 ratio to group conditions as depicted in Figure 6. Based on the ROC analyses we estimate a potential 50% non-response rate for both the online and weekend condensed groups. After the Week 4 assessment of response criteria, non-responders will also be randomized to second stage interventions with a 1:1 allocation.

More specifically, power needed to be estimated by addressing the restricted randomization scheme and appropriate weighting of the overrepresentation of responders and underrepresentation of nonresponders. We employed procedures outlined by Oetting and colleagues for estimating power in SMART trial designs. As recommended, we specified an alpha level of .10 and power of .80. The first main research question (2a) addresses main effects of initial stage randomization,

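### Section 3.1 designates no outcome, only the week-4 tailoring variable, and Section 17.1 runs the primary evaluation on unranked constructs with no primary time point and no multiplicity rule

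*Combined protocol and SAP*

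**What the plan says.** Section 3.1 carries the primary endpoint heading but describes the adaptive design. The one variable it designates is the decision input: "the primary tailoring variable is parental locus of control, a key variable shown in our prior studies to predict change in observed parenting effectiveness". Other outcomes appear there only as things this score predicts.

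Section 5.2 fixes when the Parenting Locus of Control (PLOC) score is taken: "The PLOC will be used as the primary tailoring variable measure by all participants at 4 weeks following the start of the intervention". It also says what follows from a low or missing score: "threshold on the PLOC or does not complete the PLOC, that family will be re-randomized to the second stage ADAPT interventions". Section 17.2 gives the same order: "After the Week 4 assessment of response criteria, non-responders will also be randomized to second stage interventions with a 1:1 allocation".

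For outcomes, Section 5.1 sets out to study "effects of ADAPT modalities and sequences/timing on multiple behaviors and outcomes". It lists three unranked groups: family and parenting (opening "i) coercive family interactions, positive parenting, couple adjustment, and co", the last item being co-parenting), parent symptoms, and child adjustment.

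Section 17.1 plans the primary efficacy analyses "using pre-post assessment scores for parent and child adjustment constructs" and does not say which follow-up is the post score. Section 5.3 offers three: T2 at 6 months, T3 at 12 and T4 at 24.

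Section 17.2 poses three main questions: 2a (first stage), 2b (second stage, non-responders) and 2c (best strategy). It states a two-sided alpha of .05 and then an alpha of .10. Neither section contains a hierarchy, gatekeeping or adjustment.

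**The concern.** A primary endpoint fixes, before the data are seen, which result answers the trial's question. Here that place is taken by a variable measured before the second randomization. It could describe a short-term first-stage effect, but not a booster or strategy effect.

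The protocol calls the trial Phase III and its main analysis primary. Yet a team following it exactly could report whichever construct and follow-up time looked best. The best strategy could also differ between outcomes, with no rule to decide. A per-test alpha, whichever of the two applies, does not bound the error of a conclusion chosen that way.

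**Working it through.** **1. The plan's own figures.** The Section 17.2 table gives minimally detectable effects (MDEs) at .80 power and 10% attrition of .324 (2a, N = 473) and .458 (2b, N = 236). The standard 1:1 formula with SD 1 is MDE = (z for alpha + z for power) × √(4/N).
- Two-sided .10: (1.645 + 0.842) × √(4/473) = .229 for 2a, and .324 for 2b with N = 236.
- Two-sided .05: .258 and .365.

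Neither matches. Multiplying the two-sided .10 results by √2 gives .323 and .458, which agrees with the table to rounding. The 20% attrition entries (.343 and .485) also fit. The table does not explain the factor. The fit implies the .10 level with no multiplicity adjustment. The 2c formula is not given, and 2c was not reproduced.

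**2. Order of events.** First randomization, week-4 PLOC, second randomization of those who score below the cut or do not complete it, boosters, then T2 to T4. The week-4 PLOC comes before anything a booster could change.

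**3. How many constructs.** Section 5.1 lists four in its first group, three parent constructs (PTSD symptoms, depression, substance use) and two or three child constructs, depending on whether behavior and emotional problems are counted together. The total is 9 or 10. If Section 17.1 is read as covering only the parent and child groups, about six remain.

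**4. Chance of at least one false positive, one question, all nulls true.** For k independent outcomes it is 1 − (1 − α)^k. For example, 1 − .95^6 = .265 and 1 − .95^10 = .401. The correlated figures take k standard normal statistics with a common correlation, which is an assumption because the documents give none.

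| Constructs | α | Independent | Correlation .5 |
|---|---|---|---|
| 6 | .05 | 26% | 21% |
| 10 | .05 | 40% | 29% |
| 6 | .10 | 47% | 37% |
| 10 | .10 | 65% | 49% |

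At a correlation of .7, ten constructs give 21% at .05 and 37% at .10.

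**5. Two questions.** 2a and 2b rest on separate randomizations and are treated as independent: 1 − (1 − p)², with p from step 4 before rounding.
- At .05: from 37% (six constructs, correlation .5) to 64% (ten, independent).
- At .10: from 60% to 88%.

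**6. Price of controlling 2a and 2b together.** Holm over two tests at an overall two-sided .05 starts at .025 (z = 2.241).
- Standard formula: (2.241 + 0.842) × √(4/473) = .284 for 2a and .401 for 2b, against .258 and .365 at .05.
- Table's scale (× √2): about .40 and .57, against the stated .324 and .458. Part of this rise comes from moving from .10 to .05, which alone gives .364 and .516.

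**The case against.** The strongest reply has four parts.

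- **PLOC is never called an endpoint.** Sections 3.1 and 5.2 label it only as the tailoring variable. A reader might infer that the trial's primary outcome is PLOC, and the text does not say so. This stands, but it leaves the section with no endpoint at all.
- **Question 2c is not an alpha-level test as sized.** The table gives a correct-strategy probability of .95, which is selection of a best strategy. A reader might multiply ten constructs by three questions and speak of 30 tests. The documents do not support that count. Section 17.1 mentions contrasts between embedded strategies, but gives neither their number nor a threshold. This stands, so the working counts 2a and 2b only.
- **Ten constructs is the wide reading.** Section 5.2 groups parenting practice and couple adjustment apart from parent and child adjustment, which supports about six. Section 17.1 also plans data reduction, which might lower the count. This stands as a reason for a range. It does not remove the gap, because no reduced set is named.
- **Error is not uncontrolled, and the stated goal is optimization.** Per-test alphas are given, although they conflict, and the plan does not promise 5% across all outcomes. What is missing is multiplicity control. The optimization goal tempers the criticism, but the protocol still calls the trial Phase III and the analysis primary.

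**Conclusion.** The point holds in this form: no primary outcome, primary time point or multiplicity rule is designated, and the one variable in the primary endpoint section precedes the second randomization.

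On a single question the false-positive chance is 26–40% at .05 and 47–65% at .10 with independent outcomes, or 21–29% and 37–49% at correlation .5. Over 2a and 2b together it is 37–64% at .05 and 60–88% at .10. These ranges assume 6 to 10 constructs, all nulls true, equal correlation between outcomes, and independence of 2a and 2b. They leave out the choice among three follow-up times, which would add to them.

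A reader might conclude that the trial can give no confirmatory answer. That goes too far: the randomizations and planned assessments can support one if the outcome is designated before outcome analysis.

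**What to change.** **In Sections 3.1 and 17.1, before outcome analysis:**
- Designate one primary outcome measured after both stages, as a single pre-defined score at one time point, with a stated rule for two-parent families. One candidate is an observed-parenting composite from the Family Interaction Task at T3, which is already collected. The task as described yields several measures and is partly done with each parent separately, so naming the task alone would not define one endpoint. The sponsor may prefer another post-booster outcome.
- Use that outcome for 2a and 2b, and to select the best strategy in 2c.
- Make all other constructs secondary, with Holm or false discovery rate control within each domain.
- State which alpha applies. If one overall error rate is claimed for 2a and 2b, apply Holm to those two tests only and keep 2c as a selection.

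**Cost.** Wording, with no new families or measurements. The optional joint control of 2a and 2b costs sensitivity. At an overall .05 and 10% attrition, the first-step MDEs are .284 and .401 by the standard formula, or about .40 and .57 on the scale of the protocol's table. The sponsor should see both scales before choosing, since the loss is greater for the booster question.

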4.0 Study Intervention(s)/Interaction(s)

4.1 Description:

The tested formats, sequences, and doses of ADAPT include:

- (1) Begin with ADAPT Online. Parents exhibiting initial response receive continued access to online resources. Parents exhibiting non-response are stepped-up to booster individual face-to-face ADAPT.
- (2) Begin with ADAPT Online. Parents exhibiting initial response receive continued access to online resources. Parents exhibiting non-response are stepped-up to booster group-based ADAPT.
- (3) Begin with ADAPT condensed group (with online support). Parents exhibiting initial response receive continued access to online resources. Parents exhibiting non-response are stepped to booster group-based ADAPT.
- (4) Begin with ADAPT condensed group (with online support). Parents exhibiting initial response continue access to online resources. Parents exhibiting non-response are stepped-up to booster group-based ADAPT.

This approach allows families who do not need intensive services to receive appropriately brief services. Those higher-need families receive more intensive services.

5.0 Procedures Involved

5.1 Study Design:

To address Aim 1, we will compress the ADAPT group and individual curriculum, through consultation with service members, spouse, and content experts. Curriculum adjustments will be initially made based on installation staff feedback during two weeks of facilitator training, as well as feedback obtained from non-study participants (military parents) during mock-workshops and groups led by newly trained facilitators. Focus groups will be convened after the first workshop is delivered. Findings will be shared as noted below and further modifications of the curriculum will be made, if deemed appropriate.

Focus Groups: We will conduct two focus groups with participating study families, one group with 12 Special Operations (SO) participants and one group with 12 Regular Army (RA) participants, both at Fort Bragg, NC. To ensure gender sensitivity, we will recruit and ask similar questions of mothers and fathers.

Study participants (parents) who have already received the study intervention (N = 40 families) will be sent an email asking if they would be available for a Focus Group to collect feedback on (i) relevance of materials for active duty and high OPTEMPO populations, (ii) examples of key parenting challenges related to high OPTEMPO, and (iii) preferences for specific program formats (length/time of days/days of week). If participants are not able to attend an in person focus group, an opportunity to share this feedback by phone with study staff will be offered. With permission, anecdotes about deployment will be anonymized and incorporated into scripts as teaching vignettes and role plays. Focus groups and phone interviews will be scheduled when it is convenient for participants.

After reviewing the report of the focus group results, our Expert Panel will gather via videoconference (Month 4). Panel experts will weigh in on the results and be provided with two weeks to provide written recommendations. Expert panel and focus group feedback will inform (i) how to best compress key ADAPT skills, and (ii) address issues specific to high deployment OPTEMPO conditions. The focus group data and panel feedback will be used to adjust components for the SMART that do not fundamentally change the core components while increasing our program deliverers (facilitators) awareness of challenges facing active duty populations for future program delivery.

To address Aims 2,3,4: Among 210 SO and 315 RA families (i.e., total N=525 families) with 5-12 year-old children, we will examine effects of ADAPT modalities and sequences/timing on multiple behaviors and outcomes (i.e., (i) coercive family interactions, positive parenting, couple adjustment, and co-

parenting, (ii) parents PTSD symptoms, depression symptoms, substance use, (iii) child behavior and emotional problems, and positive adjustment, by conducting a 2-stage SMART, and (iv) document participation, satisfaction, and fidelity. To assess behaviors and outcomes, we will administer and collect a series of assessments (Table 1 appendix) at 4 timepoints.

For Aims 2, 3, and 4, we will use a 2-stage SMART design to examine the optimal sequence, dosage, and delivery formats of ADAPT for active duty military families living in a range of operational tempo contexts. We will recruit a total of 525 families living on three installations: Fort Bragg (North Carolina), Fort Campbell (Kentucky) and Forts Belvoir/Myer, with 210 families recruited from Fort Bragg and Fort Campbell and 105 from Forts Belvoir/Myer.

5.2 Study Procedures:

Subjects for this study include: (I) 525 active duty clinical trial participants recruited from 4 bases who will be randomized to first stage (brief interventions) and second stage (more intensive booster ADAPT programs for families who do not benefit from the first stage interventions); (II) Twelve current study families (N = 24) who will participate in focus groups; (III) 525 children participants between the ages of 5-12 of clinical trial participants who will be asked to participate in assessments only; (IV) Up to 1890 teachers who will be asked to complete the Behavior Assessment System for Children, Second Edition (BASC-3) each yr that the child is in the study (usually 3 grades)

Focus group Participants

We will hold two focus groups with study parents to inform program modifications. Each focus group will consist of 12 participants, one group Special Operations (SO) participants and one group Regular Army (RA) participants, both on Fort Bragg, NC.

Clinical Trial Participants

Active duty families will be living in a range of operational tempo (OPTEMPO) contexts (i.e., Regular Army/RA and Special Operations/SO) on one of four military installations. All participants will be in units with deployments occurring during the study period. 525 families will be recruited from target bases as follows: (a) Fort Bragg, NC – 210 families recruited, including 105 SO and 105 RA. (b) Forts Belvoir/Myer, VA – 105 Active Duty families recruited. (c) Fort Campbell, KY– 210 families recruited, including 105 SO and 105 RA.

Clinical Trial Participants will be asked to do the following:

- (1) Complete assessments at four time points. Assessments are listed and described below and included on the final page of the protocol.
 - a. T1 (baseline (BL) and prior to the start of the intervention); both on-line and in-home data is collected from families; child self-report measures will be gathered and are standardized with children over 5.
 - b. Responder Checkpoint – Parent Locus of Control 22-item questionnaire completed by parents 4 weeks after they start the intervention

- c. T2 (6 months following baseline); only online parent data will be gathered, (no in-home assessment)
 - d. T3 (12 months following BL, i.e. following the end of the reintegration session(s) and program completion); both on-line and in-home data is collected from families, child self-report measures will be gathered from children over age 5.
 - e. T4 (24 months after BL); both on-line and in-home data is collected from families, child self-report measures will be gathered from children over age 5.
2. Participate in videotaped (with audio) in-home parent-child interaction tasks lasting a total of 30 minutes at three time points (BL/T1, T3, and T4). These interaction tasks are administered and videotaped by trained assessment technicians in the participants' homes. If preferred, participants may complete assessments outside the home at project offices. Video and audio of study participants will be accessed only by the investigators and trained members of the coding team.
3. Fill out online questionnaires at the time of in-home assessments (BL/T1, T3, and T4).

Note: childcare provided by study staff is offered during in-home assessments for siblings. If study staff are not available to provide childcare, a \$30 gift card stipend will be offered to the family so that they can arrange their own childcare.

All measures are listed in the table below and include: (1) The Parenting Locus of Control (PLOC); (2) The Family Interaction Task (FIT); (3) The Alabama Parenting Questionnaire (APQ-22); (4) Deviant Peer Association (PERS); (5) The Behavior Assessment System for Children, Third Edition (BASC-3); (6) Coping with Children's Negative Emotions (CCNES); (7) The UCLA PTSD-Reaction Index (PTSD-RI); (8) the Children's Depression Inventory (CDI); (9) Describing Friends; (10) PTSD Checklist (PCL); (9) Difficulties in Emotion Regulation Scale (DERS); (11) The Five Facet Mindfulness Questionnaire (FFMQ); (12) Receipt of Help (PSI); (13) Alcohol Use Disorders Identification Test (AUDIT); (14) Center for Epidemiologic Studies Depression Scale (CESD); (15) Deployment Risk and Resilience Inventory (DRRI); (16) Differential Ability Scales (DAS-7); (17) Moral Injury (MIES); (18) Parenting Mindfulness (IEM-P); Parenting Identity; (19) NIH Toolbox Flanker (EF – Inhibitory Control); (20) NIH Toolbox Peabody Picture Vocabulary Test; (21) Deviant Peer Association (TPRISK) Process measures include: satisfaction questionnaires, attendance, practice, online use, and coder ratings to measure fidelity.

(i) The PLOC will be used as the primary tailoring variable measure by all participants at 4 weeks following the start of the intervention (when condensed group or online programming is completed). The PLOC is a 22-item questionnaire that takes about 5 minutes. A link sent to each parent's email address will provide access to the questionnaire. The results of this questionnaire will determine responder status for each individual. If a parent scores below the cut-score

threshold on the PLOC or does not complete the PLOC, that family will be re-randomized to the second stage ADAPT interventions.

(ii) Context measures:

- (a) Demographic information such as gender, age, racial, and ethnic identity for parent and child;
- (b) employment;
- (c) income,
- (d) date/s and number of deployments for parents. Number and length of deployments will be assessed from 3 open-ended questions to obtain information about the extent of respondents' deployment history. Combat exposure will be measured using subscales from the DRRI, an ecologically valid instrument for assessing risk and resilience factors among military personnel participating in recent and current deployments.

(iii) Parenting practice measures:

- (a) Observations of parents and children using the Family Interaction Task (FIT) will last approximately 30 minutes. The child will complete a problem-solving task and discuss an emotional deployment challenge with each participating parent separately. The other tasks include: planning a fun family activity, a game/teaching task, and a monitoring task in which parents seek information about an activity in which the child was unsupervised. If two parents are participating in the study, they will also problem solve a parenting challenge in their household. Coder ratings of these tasks yield reliable and valid measures of parenting practices that have predictive validity for parent and child;
- (b) Self report measures including the APQ short form, a widely used 9 item measure of parenting practices validated in military and community samples.

(iv) Child Adjustment measures:

- (a) The BASC-3 teacher, parent, and child self-report. The BASC is a multi-dimensional system assessing broad domains of externalizing problems, internalizing problems, and school problems as well as adaptive skills. Items are rated on a 4-point scale. Gender-specific normative scores are provided. Parents rate child behaviors using the parent version of the BASC2 while teachers use the Teacher Report Form. The child self-report version has been validated and demonstrated responsive to intervention and will target children ages 5 and older;
- (b) The CDI will be used to measure child distress. The CDI is a 27-item symptom-oriented index, validated with 7-17 year olds, has been shown to correlate highly with similar measures of depression, and is sensitive to change over time;
- (c) The PTSD-RI is a 20-item child interview assessing post-traumatic stress reactions. The child is asked to endorse how frequently each reaction occurs on a four-point scale. Scores are strongly associated with diagnostic measures of PTSD;
- (d) Describing Friends is a 5 item index to measure deviant peer association, used in previous ADAPT studies and is sensitive to change as a result of the intervention;

(v) Parent Adjustment measures:

- (a) The PCL is a 17 item, clinically validated, self-report screening tool used to assess the presence and severity of PTSD symptoms as defined the DSM-IV;
- (b) The CESD - 20 items - assesses depressive mood, motor, and somatic difficulties in the general population and has been widely used and validated in national health surveys;
- (c) The AUDIT is a self-report measure developed by the World Health Organization as a fast, reliable way to screen for excessive drinking and validated in over 2 decades of research with multinational samples and deemed effective for early identification in military populations;
- (d) The FFMQ is a 39-item questionnaire used to assess parent mindfulness with 5 subscales (observing, describing, acting with awareness, non-judging, and non-reactivity);
- (e) The DERS is a 36-item questionnaire used to assess emotion regulation/dysregulation in adults in six domains;
- (f) Receipt of Help (5 items) was developed for the National Survey of Families and Households and assesses the degree to which parents receive practical help using a scale from low to high.

(vi) Couple Adjustment measures:

- (a) The DAS-7 Short version is a 7 item scale assessing couple adjustment. The DAS-7 has well-established criterion validity and discriminant validity.

4. Participate in one randomly assigned intervention:

a. ADAPT Online. Participants will have access to the full ADAPT website (12 modules, online discussion forum). Participants are directed to the first ADAPT session, and as each session is completed (all materials in a session opened by at least one parent) families receive a personalized congratulations email and continue to the next module. Participants may see the entire program on the ADAPT dashboard; they are encouraged to proceed in the specified order. Each online session consists of a skills video (demonstrating a specific skill), a practice video (modeling how parents practice skills with child(ren)), downloadable summaries of key skills, fillable PDF forms with home practice assignments, a knowledge quiz, and downloadable mindfulness exercises that can be played directly from the ADAPT site as well as from smartphones, tablets, and computers. Participants are compensated at the end of their time period according to the portion of the modules completed. In addition, they are encouraged to respond to the 7 questions prompted by the online facilitator. To encourage this exchange, participants who respond will be entered into a drawing for a \$100 gift card (up to 7 entries). At the end of the online group, one winner will be drawn at random. For example, if there are 10 participants in Cohort 1 and all 10 of them answer each of the 7 facilitator questions then there would be 70 entries for the drawing (10 participants x 7 entries each). This would give each participant a 7% chance that their name would be drawn to receive a \$100 gift card;

b. Condensed group-based ADAPT. Participants will meet for 2 week/weekend days two weeks apart, for 6 hours each day (excluding holidays) at a time convenient to participants. Dinner and childcare are provided. If families are unable to or elect not to register for CYS childcare on the installation or the minimum number of children for CYS childcare is not met, participants will be offered a \$50 stipend in the form of a gift card to arrange their own childcare in order to attend workshop;

